I assure the HIC that the principal investigator and all members of the research team are qualified by education, training, licensure and/or experience to assume participation in the conduct of this research trial. I also assure that the principal investigator has departmental support and sufficient resources to conduct this trial appropriately.
Chair Name (PRINT) and Signature Date
Chair Name (FRIVI) and Signature
Department
YNHH Human Subjects Protection Administrator Assurance Statement
Required when the study is conducted solely at YNHH by YNHH health care providers.
As Human Subject Protection Administrator (HSPA) for YNHH, I certify that:
I have read a copy of the protocol and approve it being conducted at YNHH.
 I agree to notify the IRB if I am aware of any real or apparent institutional conflict of interest. The principal investigator of this study is qualified to serve as P.I. and has the support of the hospital
for this research project.
YNHH HSPA Name (PRINT) and Signature Date

SECTION V: RESEARCH PLAN

1. **Statement of Purpose:** State the scientific aim(s) of the study, or the hypotheses to be tested.

This is a four week, randomized, placebo controlled, crossover trial comparing cannabidiol (CBD) to placebo in outpatients with psychotic disorder within their first five years of disease onset. We hypothesize that treatment with CBD will result in:

- a. Primary Hypotheses:
 - i. Improvement evidenced by a reduction in scores on the Positive and Negative Syndrome Scale for Schizophrenia (PANSS).
 - ii. Improvement evidenced by a reduction in the Clinical Global Impression of Severity scale (CGI).
- b. Secondary Hypothesis:
 - i. Greater improvement in functioning as measured on the "Patient Assessment of Own Functioning Inventory: (PAOFI) and the Quality of Life Scale (QLS)
 - ii. No worsening of depressive symptoms or suicidality as measured on the CDSS and CSSRS.
- c. Exploratory Hypotheses:
 - i. Exploration of the effect of CBD on EEG recordings of MMN and P300 amplitude and latency, known endophenotypes/biomarkers of Schizophrenia
- 2. **Background:** Describe the background information that led to the plan for this project. Provide references to support the expectation of obtaining useful scientific data.

There is a need to develop anti-psychotic therapeutics with novel mechanisms of action and fewer side effects:

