Visit VIII: One close-out visit will be conducted after Visit VII in Period 2 for lab review and safety follow up.

Note: Visits II-VI can be split into two visits, which must be completed within +/- 3 days of each other based on the subject's availability.

Outpatient Medication Compliance: Medication compliance will be monitored throughout each study period by self-report and vial counts at study visits and using the *Cellphone Assisted*Page 12 of 40

APPROVED BY THE YALE UNIVERSITY IRB 5/17/2017 VALID THROUGH 5/6/2018 Remote Observation of Medication Adherence (CAROMA). CAROMA may be used 1-2 times per day during the treatment period to confirm compliance. Flexible scheduling will be maintained regarding time and days of CAROMA depending on subject reliability, availability and frequency of in person visits. Subjects will be provided with a cellphone with the hardware, software and service necessary to transmit high quality video. Prior to randomization, the subject will be trained how to use the phone and also trained on the compliance protocol. For this, the subject will be placed in one clinic office with the phone. A research staff member will video call the subject from another location in the clinic and observe the subject consuming a syringe of water. Once successfully trained in the clinic, the subjects will be loaned the phone to take home for one trial CAROMA visit. This is to ensure that 1) the in-clinic training extends to the home, and 2) that the subject has adequate cellular service at home. Within a time period predetermined by agreement, subjects will be called on the cell phone and will be observed removing study medication from the packaging and swallowing the medication. The research assistant will log visual confirmation of compliance. Subjects will receive additional compensation for CAROMA visits as outlined in the "Economic Considerations" section below. Subjects who are not contactable will be assumed to be noncompliant for that visit and will not receive payment for the missed CAROMA visits.

Finally, compliance will also be confirmed by measuring CBD levels in plasma from blood sampled at regular intervals throughout the study.

Study Procedures:

Safety Assessment: during each visit. This will include assessment of psychiatric status, assessment of adverse events, vital signs, and safety labs (CBC, Chem 19, urinalysis, and urine toxicology).

Outcome measures:

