- e. Worsening of psychosis: Participation in this study may be associated with worsening of psychosis especially in those individuals who are not on any other antipsychotics. Subjects will be evaluated on a weekly basis in face-to-face meeting with study staff. Psychotic symptoms, mood symptoms and suicidality will be assessed at each of these meetings. Further, subjects will be contacted approximately 5 times per week using CAROMA for the confirmation of compliance. During each of these visits, subjects will be asked if they have noticed any worsening of symptoms or any new side effects. If subjects report that they do notice a worsening of symptoms or side effects, this will be evaluated by an investigator on the team and subject will be asked to come into the clinic to be evaluated if clinically indicated. Subjects are well aware that in case of significant worsening of symptoms/ emergence of SI/HI, they may be escorted to the ER or admitted to an inpatient unit.
- **f. Risk of blood draws: B**lood will be drawn weekly during the study to monitor medication levels as well as safety labs. There are usually no serious medical problems with blood drawing, but there may be pain at the venipuncture site or bruising or infection may occur.
- **g. Risks of EEG:** EEG is a non-invasive assessment. There are minimal risks associated with EEG/ERP recording. Traditionally, scalp abrasion has been used to improve

signal impedance at the electrode site. The EEG/ERP system used in this laboratory is a high-impedance system and does not require scalp abrasion to obtain clean recording. A conductive gel is applied, which can be easily washed out of the subject's hair with warm water. A shower facility for hair washing and sterile linens are available in the laboratory. Electrode caps and sensors will be washed and sterilized between subjects to minimize the risk of transmitting infection.

Potential benefits: Subjects will receive no direct benefit from this study. Potential benefits may include improvement in psychotic and cognitive symptoms, decreased negative symptoms, avoidance of potential side effects from usual anti-psychotic medications themselves or from dose increases of such medications. Overall, the development of novel anti-psychotics will provide benefit to the schizophrenia population as a whole.

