DSMB: A Data Safety Monitoring Board is being assembled for this study. Unblinded safety data will be provided to the committee for monitoring purposes, in a meeting that will be held approximately every 6 months. DSMB reports will be provided to the HIC.

11. Statistical Considerations:

General Strategy:

All outcomes will be summarized descriptively and assessed for normality prior to analysis using normal probability plots and Kolmogorov test statistics. Transformations or nonparametric analyses will be performed as necessary. All tests will be two-sided and considered statistically significant at alpha=.05. Post-hoc comparisons will be performed as appropriate and significance levels for secondary analyses will be adjusted for multiple tests using the Bonferroni correction. All analyses will be performed using SAS, version 9.3 (SAS Institute Inc., Cary, NC).

Linear mixed models will be used assess symptom improvement as measured by the PANSS (primary hypothesis) and CGI. In these models group (CBD vs. placebo) and time (see study time points) will be modeled as within-subjects factor. Oder effects will also be tested. Least squares means and standard errors will be calculated in the mixed model and plotted to interpret significant effect. A significant group by time interaction explained by reduced symptoms over time due to CBD treatment will be supportive of our hypothesis. In the above models, the best fitting variance-covariance structure will be selected based on information criteria. The mixed effects approach is advantageous in that it is unaffected by randomly missing data and allows greater flexibility in modeling the correlation structure of repeated measures data [31]. Similar mixed models as described above will be employed to evaluate secondary outcomes (e.g., PAOFI, EEG parameters).

Power Analysis:

We will recruit 36 subjects and randomly assign 18 to receive either CBD followed by placebo (order 1) or placebo followed by CBD (order 2). Based on a within-subjects design and a two-tailed alpha=0.05, 36 subjects will provide 80% power to detect moderate treatment effects as small as d'=0.49. This compares favorably with the effects (d=0.7) observed by Leweke in their study comparing CBD to amisulpiride in schizophrenia patients.

SECTION VI: RESEARCH INVOLVING DRUGS, BIOLOGICS, RADIOTRACERS, PLACEBOS AND DEVICES

If this section (or one of its parts, A or B) is not applicable, state N/A and delete the rest of the section.

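### The CDSS that secondary hypothesis b.ii relies on is not scheduled, and the plan gives no basis for concluding no worsening from a non-significant result

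*Combined protocol and SAP*

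**What the plan says.** **Hypothesis.** Section V, item 1 (Statement of Purpose), secondary hypothesis ii reads "No worsening of depressive symptoms or suicidality as measured on the CDSS and CSSRS". This is the only place where the CDSS appears in the available text.

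**Collection.** The Outcome measures list in Section V has twelve numbered entries. The CSSRS is item 4 (Visits I-VI); the QLS and PAOFI, which serve the other secondary hypothesis, are items 5 and 6 (Visits II-VI). The CDSS is not listed. On the safety assessment made at each visit, Study Procedures says "This will include assessment of psychiatric status, assessment of adverse events, vital signs, and safety labs", with no depression scale. Item 8 (Risks), part e, says of the weekly face-to-face visits: "Psychotic symptoms, mood symptoms and suicidality will be assessed at each of these meetings". Item 9 (Minimizing Risks) repeats this. Neither names an instrument.

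**Analysis.** Section V, item 11 (General Strategy) sets these rules:
- "All tests will be two-sided and considered statistically significant at alpha=.05".
- "significance levels for secondary analyses will be adjusted for multiple tests using the Bonferroni correction". The number of tests in the family is not given.
- "Similar mixed models as described above will be employed to evaluate secondary outcomes". The examples given are the PAOFI and EEG parameters; the CDSS and CSSRS are not named.
- The one stated criterion of success: "A significant group by time interaction explained by reduced symptoms over time due to CBD treatment will be supportive of our hypothesis".
- "Least squares means and standard errors will be calculated in the mixed model and plotted to interpret significant effect".

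The section also promises descriptive summaries of all outcomes. It mentions no confidence interval, margin or other rule for a claim of no worsening.

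**The concern.** There are two linked gaps.

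The first is in the data. The hypothesis depends on a named scale that no schedule tells staff to administer. An unstructured weekly check of mood can protect the subject, but it does not produce CDSS scores, and scores missed during the trial cannot be recovered later.

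The second is in the inference. A claim of no worsening needs evidence that excludes worsening of some size. The planned test looks for a difference. When it is non-significant, it cannot separate worsening that has been excluded from worsening that was not detected. A Bonferroni correction protects against false claims of benefit; applied to a harm comparison, it raises the bar for noticing harm and so makes a reassuring non-significant result more likely.

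What is at stake is the conclusion reported for this secondary hypothesis. The primary PANSS and CGI analyses are untouched.

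**Working it through.** **Inputs from the documents.** 36 subjects, within-subjects design, two-tailed alpha 0.05, 80% power at d' = 0.49 (Power Analysis); 36 completers intended (Section VII, Targeted Enrollment). Four secondary scales are named in the Statement of Purpose: PAOFI, QLS, CDSS and CSSRS.

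**Assumptions.** A single paired CBD-minus-placebo contrast at week 4; effects in SD of the within-subject difference; a Bonferroni family of the four named scales, so alpha = 0.05/4 = 0.0125. The figures illustrate the CDSS only.

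**Formula.** With n = 36, df = 35 and true effect d, the test statistic is noncentral t with noncentrality d × √36 = 6d. Power is the probability that it exceeds the two-sided critical value in absolute size. The miss rate is 1 − power.

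**The plan's own figure.** d = 0.49 gives noncentrality 6 × 0.49 = 2.94. At alpha 0.05, power is 81.6%, which agrees with the stated 80%. So d' behaves as an effect in SD of the within-subject difference.

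**Chance that a true worsening is non-significant:**

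| True worsening (SD) | Noncentrality | alpha 0.05 | alpha 0.0125 |
|---|---|---|---|
| 0.30 | 1.80 | 58% | 78% |
| 0.40 | 2.40 | 35% | 58% |
| 0.49 | 2.94 | 18% | 38% |

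**Smallest observed worsening that reaches significance** (critical t divided by 6): 0.34 SD at alpha 0.05 and 0.44 SD at 0.0125.

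**One possible result.** An observed worsening of 0.30 SD gives t = 0.30 × 6 = 1.80 and p = 0.08. The 95% confidence interval is 0.30 ± 0.338, or −0.04 to 0.64 SD. This is non-significant even without Bonferroni, yet it does not exclude a worsening of 0.6 SD.

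**Would a margin solve it?** The documents give no margin, so a range is assumed. With a true difference of zero and one-sided alpha 0.025, power at n = 36 is about 42% for a margin of 0.3 SD and 65% for 0.4 SD. Reaching 80% would need 90 and 52 subjects respectively.

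**The case against.** The strongest reply is that this is a safety-type secondary hypothesis in a 36-subject trial, and that subjects are watched closely: mood and suicidality are assessed weekly, the CSSRS is collected at Visits I-VI, and a DSMB sees unblinded safety data about every 6 months. That stands. A reader might infer that depression goes unmonitored; the documents do not support this. The gap is in CDSS data and in the conclusion drawn from them.

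Other tempting readings also go too far:

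- *The plan treats non-significance as proof of no worsening.* It does not say so. It is silent on how a non-significant result will be read.
- *Nothing in the plan could support the hypothesis.* A significant reduction on the CDSS under CBD would support it. Only the non-significant case lacks a rule.
- *The comparator is unstated.* The hypotheses sit under a stem describing a comparison of CBD with placebo, and the General Strategy defines the group factor as CBD versus placebo.
- *No estimates will be available.* Descriptive summaries are promised for every outcome, and least squares means with standard errors will be calculated. What is missing is a commitment to a by-treatment estimate with an interval when the result is not significant.

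It is also fair to say that the analysis of these two scales is inferred, since the General Strategy does not name them. They are secondary by the Statement of Purpose, so its rule for secondary outcomes is the natural reading.

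The arithmetic has limits. A paired contrast is not the planned group by time test, and a repeated-measures model could be somewhat more precise. The SD figures do not carry over to the CSSRS, an interview on ideation and behaviour. Without a CDSS standard deviation in the documents, their clinical size is unknown.

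**Conclusion.** The point holds in two parts. First, the CDSS is named in a secondary hypothesis but appears in no outcome list, schedule or safety assessment in the available text, so following the plan could yield no CDSS data. Some pages were not available for review; nothing in the remaining text points to a CDSS schedule there. Second, the rule for secondary outcomes gives no basis for concluding no worsening from a non-significant result, and the Bonferroni correction makes harm harder to flag.

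Under the stated assumptions, the correction over four scales raises the chance of missing a true 0.3 SD worsening by 20 percentage points (78 − 58), and likewise for 0.49 SD (38 − 18). These figures depend on the assumed family of four, which the plan does not define.

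This should be corrected, but it does not threaten the primary result.

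**What to change.** 1. Add the CDSS to the Outcome measures list with visits, for example alongside the CSSRS at Visits I-VI.
2. Report the CBD-minus-placebo CDSS estimate from the mixed model with an unadjusted 95% confidence interval, whether or not it is significant.
3. Take the CDSS and CSSRS harm comparisons out of the Bonferroni family.
4. Report CSSRS ideation and behaviour descriptively by treatment.
5. Restate hypothesis b.ii as safety estimation, and say that non-significance will not be read as no worsening.

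A non-inferiority margin for the CDSS is possible but not advised as the default, given its low power at this sample size. If one is used, it should be clinically justified, fixed before unblinding and not derived from the sample size.

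**Cost.** One more scale per visit: Visits I-VI in Period 1 and II-VI in Period 2 make 6 + 5 = 11 administrations per subject if screening is counted once. The rest is wording. Unadjusted harm comparisons will produce more chance signals, and b.ii becomes a weaker statement, an estimate with its uncertainty.

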Medical and Psychiatric Evaluation: Once written informed consent has been obtained, the diagnosis will be confirmed by a Structured Clinical Interview for DSM IV (SCID). A detailed medical and psychiatric history, physical examination (including vital signs, height, and weight), an electrocardiogram, and laboratory assessments (standard screening blood tests: CBC with differential and platelet count, electrolytes, creatinine, BUN, liver enzymes, T4, calcium, phosphate, TSH, and magnesium levels) will be performed. In addition, a full lipid profile, fasting glucose and insulin levels will be obtained. A pregnancy test will be done in all premenopausal women. A routine urinalysis and drug screen will be done as part of the screening process.

Subjects will be administered the PANSS and motor side effects scales (AIMS, Barnes akathisia scale, Simpson Angus scale). IQ will be measured at screening using the Wechsler Test of Adult Reading (WTAR). Subjects will also be asked to provide an informant who can be contacted to collect clinical and safety information relevant to the outcome measures on each visit. This could be a clinician or a family member/friend who sees the patient at least on a weekly basis.

Study Design: In this 2 period cross over design, subjects will be randomized in a 1:1 ratio to receive either: **Order 1**: CBD (Period 1) followed by placebo (Period 2) or **Order 2**: Placebo (Period 1) followed by CBD (Period 2) under double-blind conditions. The 2 study periods will be separated by a washout of at least 2 weeks. During each period subjects will receive study medications (CBD [total 800mg/day] or placebo) for a period of 4 weeks. This dose is within the dose range of doses that have been shown to be effective and safe. Randomization to the order of medication assignment will be stratified by baseline PANSS scores.

Study Visits:

Subjects will have the following visits during each period except for Visit I (screening), which will occur only at the beginning of their participation in the study:

Visit I: Screening (At least two visits: Visit Ia and Visit Ib.)

Visit II: Baseline: Will initiate treatment with study drug following baseline assessments.

(Visits III, IV, V: Weekly clinical evaluation and study medication refill)

Visit III: (Week 1)

Visit IV: (Week 2)

Visit V: (Week 3)

Visit VI: (Week 4): End of treatment period visit

Visit VII: Safety Follow up at week 5.

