6. **Inclusion/Exclusion Criteria:** What are the criteria used to determine subject inclusion or exclusion?

Inclusion Criteria:

- 1. Primary psychotic disorder (Schizophrenia, Schizoaffective disorder, etc.)
- **2.** Age 18-65
- **3.** Capable of providing informed consent
- **4.** Within approximately five years of onset of psychosis/ presentation to treatment for psychosis

Exclusion Criteria:

- 1. Other current major psychiatric diagnoses that require pharmacological treatment (example: PTSD). Some diagnoses will be allowed at the PI discretion (example: Adjustment disorder)
- 2. Current substance dependence (other than nicotine or cannabis)
- **3.** Serious medical or neurological illness or treatment for a medical disorder that could interfere with study participation as determined by principal investigator
- **4.** History of significant head injury/trauma as determined by principal investigator
- **5.** Women who are pregnant, nursing or unwilling to use appropriate birth control measures during study participation
- **6.** Inability to complete neuropsychological tests
- 7. History of treatment resistance or current treatment with clozapine
- **8.** Current treatment with investigational agents or participation in another clinical trial that may affect outcome measures
- 7. How will **eligibility** be determined, and by whom?

Subjects may first undergo a phone screen to initially determine eligibility. Information collected during the phone screen will only be used in the event that the subject continues to participate in the study.

After determining initial eligibility, research staff will provide a brief description of the research and the subject will present to the clinic for the screening procedures described above. Once all screening procedures have been collected, research staff as well as the principal investigator will review all relevant information and determine, based on the inclusion and exclusion criteria, if the subject will continue with the remaining study procedures. Subjects already on antipsychotics or other medications will continue use of the medications while participating in the current study. Subjects will not be taken off their antipsychotic medications for participation in this study.

8. **Risks:** Participation in this study may be associated with risks related to:

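### The only pregnancy test named is at once-only screening, so Period 2 dosing starts at least 6 weeks after the first dose with no scheduled retest

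*Combined protocol and SAP*

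**What the plan says.** Four parts of Section V of the combined protocol and SAP bear on this.

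- **Exclusion criteria (item 6, criterion 5).** The excluded group is "Women who are pregnant, nursing or unwilling to use appropriate birth control measures during study participation".
- **Medical and Psychiatric Evaluation.** After consent, in the paragraph that lists the screening blood tests: "A pregnancy test will be done in all premenopausal women". The next sentence reads "A routine urinalysis and drug screen will be done as part of the screening process".
- **Study Design and Study Visits.** Each period gives study medication "for a period of 4 weeks", and "The 2 study periods will be separated by a washout of at least 2 weeks". The visits take place in each period "except for Visit I (screening), which will occur only at the beginning of their participation in the study". Dosing in each period opens at baseline: "Visit II: Baseline: Will initiate treatment with study drug following baseline assessments".
- **Study Procedures, Safety Assessment.** At each visit the assessment covers psychiatric status, adverse events, vital signs and "safety labs (CBC, Chem 19, urinalysis, and urine toxicology"; the list ends there.

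No other pregnancy test appears in the text available. Birth control is mentioned only in criterion 5.

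**The concern.** In a crossover trial each participant starts blinded study drug twice. This protocol checks pregnancy once, before the first start. Urinalysis and urine toxicology are done at screening and again at every visit; the pregnancy test is not carried forward in the same way. A conception after screening, whether before Period 1, during it or in the washout, would meet no scheduled test before Period 2 drug is dispensed.

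What is at stake is exposure to an investigational drug in pregnancy. The protocol runs under an IND, rates the study as moderate risk, and includes congenital anomaly in its definition of a grade 3 adverse event. Its sections on risks and on minimizing risks do not mention pregnancy, so they offer no alternative safeguard. Order 2 is the sequence most affected, because its first CBD dose is the one furthest from the only test.

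**Working it through.** The plan states no figure for this interval, so there is none to reproduce. The check has two steps: locate the test in the schedule, then do the timeline arithmetic from the plan's own durations.

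**Step 1: where testing is scheduled**

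| Point in the study | Urinalysis and urine drug testing | Pregnancy test |
|---|---|---|
| Screening (Visit I, once only) | Yes | Yes |
| Period 1 baseline (Visit II) | Yes, as part of every visit | Not named |
| Period 1, later visits | Yes, as part of every visit | Not named |
| Period 2 baseline (Visit II) | Yes, as part of every visit | Not named |
| Period 2, later visits | Yes, as part of every visit | Not named |

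The sentence on the pregnancy test does not itself name a visit. Its timing at screening is inferred from its paragraph and from the visit list.

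**Step 2: timeline**

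Inputs, all from Study Design and Study Visits:
- Length of a treatment period: T = 4 weeks.
- Minimum washout: W = 2 weeks, with no maximum given.
- Safety follow-up visit: week 5.
- Interval from the screening test to the first Period 1 dose: S weeks, not stated, so S is 0 or more.

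Results:
- First Period 1 dose to first Period 2 dose: T + W = 4 + 2 = at least 6 weeks. If the washout is counted from the week 5 visit, it is 5 + 2 = at least 7 weeks.
- First Period 1 dose to the end of Period 2 dosing: T + W + T = 4 + 2 + 4 = at least 10 weeks.
- Screening test to first Period 2 dose: at least S + 6 weeks.
- Screening test to first CBD dose: S weeks in Order 1, at least S + 6 weeks in Order 2.

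**Who is affected**

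The Power Analysis plans 36 subjects, hence 36 / 2 = 18 in Order 2. That count includes men and women who are not premenopausal. The plan gives no split by sex or menopausal status, so 18 is only a ceiling on the women whose first CBD dose falls in Period 2; the expected number cannot be derived.

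**With a test at Visit II of each period**

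The interval from the latest test to the first dose of either period becomes essentially zero, and to the last dose of that period about T = 4 weeks.

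**The case against.** The strongest reply is that the protocol breaks no rule of its own. In criterion 5 the closing words about study participation attach most directly to birth control. Eligibility is decided once the screening procedures are complete (Section V, item 7), and nothing says that any criterion is applied again at Period 2. Contraception is the stated control after entry. Participants are also seen weekly, asked about adverse events at each visit, and contacted about five times a week. The visit list of safety tests need not be exhaustive, and the consent form may describe a repeat test.

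Much of this stands, and it rules out several stronger readings that a reader might infer:

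- *Pregnancy is an exclusion throughout the study, so the schedule contradicts it.* No sentence says so. What runs through participation is the birth-control requirement.
- *Nothing could bring a pregnancy to light.* The weekly visits and frequent calls give a participant the chance to report one. They are not tests, however, and would not find a pregnancy of which she is unaware.
- *Eighteen women are at risk.* Eighteen is the whole of Order 2, men included.
- *Every Period 2 start is a CBD exposure.* Order 1 receives placebo in Period 2. Planned CBD exposure is 4 weeks in either order, and the 10 weeks above include placebo and washout time.
- *The screening interval is unlimited.* It is unspecified, which is a weaker statement.

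The reply does not remove the gap. No check on contraception is scheduled, and the visit and safety-test lists are present in the text and name no second pregnancy test. Because treatment is blinded, staff cannot confine a recheck to those about to start CBD.

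**Conclusion.** The point holds as a gap in the safety schedule. It is not an internal contradiction, and it does not touch the efficacy analysis. Followed as written, the schedule lets a second course of blinded study drug start at least 6 weeks after the first dose, and at least S + 6 weeks after the only named pregnancy test, where S is the unstated interval from screening to baseline. For Order 2 this is the first exposure to CBD.

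The conclusion rests on two assumptions: that the pregnancy test belongs to screening, as its place in the text indicates, and that no repeat test is described only in the consent pages, which were not available for this review. The number of women concerned is unknown, and contraception and regular contact reduce the risk by an amount that the documents do not let one estimate. The change is a cheap improvement.

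**What to change.** Reconcile Medical and Psychiatric Evaluation, Study Visits, Safety Assessment and exclusion criterion 5 in Section V as follows:

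1. Add a urine pregnancy test for premenopausal women to the Visit II baseline assessments of each period, with the result available before study drug is dispensed. Visit II may be split over two days, so the text should place the test ahead of dispensing explicitly.
2. Have the investigators state how the result bears on criterion 5, for a woman not yet dosed and for one already randomized. That is a clinical decision for them; no stopping or dosing rule is proposed here.
3. If a repeat test is already described in the consent form, bring the same wording into the protocol.

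**Cost.** Up to two urine tests per premenopausal woman, on urine already collected for urinalysis and toxicology, and a short protocol amendment. No extra visit or staff are needed. If all 36 subjects were premenopausal women, the most would be 36 × 2 = 72 tests; the true number will be lower to the extent that men and other women are enrolled.
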